## 2.8. Randomization

A computer-generated random number table was used to carry out the randomization of the patients into the two groups by an investigator who was unaware of the identity of the participants.

## 2.9. Blinding

None of the participants, care providers and outcome adjudicators were blinded to the interventions after assignment.

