#### 2.4.2. Analysis of Tissue Samples

Soft tissue punch biopsies (3 mm) were taken after wound debridement sessions at week zero (day 0) and week six (day 42). After tissue collection, samples were immediately transported to the laboratory for cellular proliferation and microbiological analyses.

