### 2.5. Outcome Measures

**2.5.1. Main Outcome Measure: Cellular Proliferation Analysis of Wound Tissue Samples.** The same senior clinician interpreted all samples to evaluate the cellular proliferation. The microvascular structure of CD31, an endothelial marker, was subjected to immunohistochemical analysis and quantification to understand the effects of debridement on neo-angiogenesis, [22]. Sections of tissue sample were immunohistochemically stained with the CD31 marker. Light microscopy was used to count the number of microvessels/endothelial cells in a standardized grid, with the results expressed as microvessel density (Leica DMD 800 morphometric system). Microvessel density was scored in proportion to the following scale: 0 (absent), 1 (low, at least one microvessel), 2 (moderate) and 3 (more than two microvessels).

To differentiate collagen content from other components, such as muscle fibrin and erythrocytes, in tissue samples we used Massons's trichome staining. Collagen content was scored according to the following scale: 0 (absent), 1 (mild), 2 (moderate) and 3 (severe) [23].

Actin staining was used to evaluate the presence of myofibroblasts involved in wound healing. These cells increase in number during wound healing. The number of stained cells was semi-quantitatively analyzed using a 0–3 scaling score (0 = no myofibroblasts, 1 = myofibroblasts in low quantities, 2 = myofibroblasts in moderate quantities, 3 = myofibroblasts in high quantities).

**2.5.2. Secondary Outcome Measure: Microbiological Analysis of Wound Tissue Samples** Specimens of wound tissue were homogenized in 0.5 mL volumes of sterile phosphate buffered saline (PBS, Sigma Aldrich, St Louis, MO). After mechanical homogenization, the specimens were seeded in Columbia agar (BD, Sparks, MD), MacConkey agar (BD), Sabouraud dextrose agar (BD) and Columbia

agar supplemented with nalidixic acid and colistin (BD) using a spiral plater Workstation (Don Whitley Scientific, Shipley, UK). Quantitative and qualitative microbiological analyses were performed after incubation of plates at 37 °C for 24 h. Isolated microorganisms were identified by standard methods and susceptibility testing was performed in accordance with Clinical and Laboratory Standards by the disk diffusion method [24]. The results were expressed as CFU per gram of tissue (CFU/g) and the limit of detection was 10 colony-forming units (CFU).

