## 2.10. Statistical analysis

Data were analyzed, based upon an intention-to-treat analysis, using the software package SPSS for iOS version 21.0 (SPSS, Inc. Chicago, IL, USA). Kolmogorov-Smirnov test was used to verify the assumption of normality of all continuous variables. Chi-square test was performed to calculate differences between groups and, if applicable, Fisher's exact test for categorical variables. Student's t-test and Mann-Whitney U test were performed for normally and abnormally distributed quantitative variables, respectively. Graphics to evaluate the differences among decrease in bacterial load and cellular proliferation between groups were done using GraphPad® for Mac OS.

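### The main-outcome histology scores are read by one unmasked clinician although slides can be coded, so arm-dependent reading would look like a treatment effect

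*Combined protocol and SAP*

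**What the plan says.** Section 2.9 says: "None of the participants, care providers and outcome adjudicators were blinded to the interventions after assignment". It makes no exception for laboratory reading.

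Section 2.5.1 makes histology the main outcome and assigns it to one reader: "The same senior clinician interpreted all samples to evaluate the cellular proliferation". Three stains are each graded 0 to 3:

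- **Collagen:** "Collagen content was scored according to the following scale: 0 (absent), 1 (mild), 2 (moderate) and 3 (severe").
- **Actin (myofibroblasts):** "The number of stained cells was semi-quantitatively analyzed", with grades of none, low, moderate and high.
- **CD31 (microvessels):** "Light microscopy was used to count the number of microvessels/endothelial cells in a standardized grid", then reduced to "0 (absent), 1 (low, at least one microvessel), 2 (moderate) and 3 (more than two microvessels").

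Under 2.4.2, biopsies are taken after debridement at week 0 and week 6, and "samples were immediately transported to the laboratory for cellular proliferation and microbiological analyses". No section mentions coded slides, a masked reader, a second reader or a check of agreement.

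Section 2.10 lists chi-square or Fisher's exact test for categorical variables and the t-test or Mann-Whitney test for quantitative ones. It does not say which class the 0-3 scores belong to, or whether week-6 scores or changes from baseline are tested. Its only reference to the comparison of proliferation concerns plots: "Graphics to evaluate the differences among decrease in bacterial load and cellular proliferation between groups".

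**The concern.** An open-label trial of two debridement methods cannot mask the patient or the operator. It can mask the person at the microscope, because the outcome is a stained section prepared away from the treatment room. Here the unmasking extends to the main outcome without need.

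The scores are open to expectation. Collagen and actin are graded on adjectives, with no limits given in the document. CD31 is less exposed because it starts from a count on a grid, but its grades still leave room for judgement: grade 1 covers one vessel or more and so overlaps grade 3, which starts above two, while grade 2 has no limits at all.

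Randomization does not protect against measurement that differs by arm after assignment. If UAW week-6 slides are read more, or less, favourably because the arm is known, the shift adds to or masks any real effect. With one reader and one reading, nothing in the data would reveal it.

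**Working it through.** The plan gives no figure for reading error, so there is none to reproduce. The sample-size statement in 2.7 supplies only the arm sizes and alpha. The check asks how far a reading shift of a given size would move the false-positive rate.

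**Inputs from the document:** 24 surgical and 27 UAW patients, alpha 0.05 (2.7); 0-3 scores (2.5.1); visits at weeks 0 and 6 (2.4.2); Mann-Whitney or chi-square (2.10).

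**Assumptions:** one marker, no true effect and a two-sided test. The base-case distribution over grades 0/1/2/3 is 15/30/35/20%, with 25/25/25/25, 35/35/20/10 and 5/15/35/45% as alternatives. A share f of the affected slides is raised one grade, capped at 3. For change scores, baseline and week 6 come from a cut bivariate normal with latent correlation 0, 0.5 or 0.8, using the base-case distribution.

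**Spurious mean difference.** A slide already at grade 3 cannot rise, so the expected shift is f × (1 − P(grade 3)). In the base case this is f × 0.80: 0.08, 0.16, 0.24 and 0.32 grade for f = 10%, 20%, 30% and 40%.

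**False-positive rate.** 20,000 simulated trials per setting, tie-corrected Mann-Whitney. The Monte Carlo standard error near 5% is √(0.05 × 0.95 / 20,000) ≈ 0.15 percentage points.

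| Setting | f = 0 | 10% | 20% | 30% | 40% |
|---|---|---|---|---|---|
| Week-6 scores, UAW raised, base case | 5.0% | 5.8% | 8.8% | 13.9% | 21.4% |
| Same, 25/25/25/25 | 4.8% | 5.9% | 7.5% | 10.7% | 15.5% |
| Same, 35/35/20/10 | 4.6% | 6.2% | 9.4% | 15.8% | 24.9% |
| Same, 5/15/35/45 | 4.7% | 5.6% | 7.3% | 11.4% | 17.1% |
| Change, only UAW week 6 raised, correlation 0 | 4.8% | 5.2% | 6.9% | 9.3% | 13.1% |
| Same, correlation 0.5 | 4.9% | 5.7% | 8.2% | 12.6% | 18.3% |
| Same, correlation 0.8 | 5.0% | 6.7% | 10.9% | 18.2% | 29.1% |

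A more concentrated distribution (10/40/40/10%) gives larger week-6 figures: 6.4%, 11.3%, 19.8% and 31.6%.

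**Patterns that do no harm.** The rate stays at 4.5 to 5.3% in three cases:

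- week-6 scores are compared and both arms are raised;
- change is analysed and week-6 slides are raised in both arms;
- change is analysed and UAW slides are raised at both visits.

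**Chi-square instead of Mann-Whitney**, on the four-grade week-6 scores: about 4-5%, 5-7%, 7-10% and 10-15% for the same four values of f.

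**The case against.** Five points can be made for the plan.

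1. **Knowledge of arm is not documented slide by slide.** Section 2.9 speaks of outcome adjudicators in general, and nothing records what the reader saw on a label or request form. This is true, but the histology reader is the adjudicator of the main outcome, so applying 2.9 to that person is the natural reading, and nothing in the document contradicts it.

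2. **Grade limits may exist in the cited sources.** The collagen scale and the CD31 method each carry a citation, and CD31 uses a named morphometric system. The claim is therefore confined to what this document states. The actin scale has no citation.

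3. **The plan does not assign Mann-Whitney to these scores.** This stands. Under chi-square, which 2.10 also allows, inflation is smaller, though it does not vanish at the larger upgrade shares.

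4. **Baseline slides may be read with knowledge of arm too**, since week-0 biopsies also follow debridement. An equal shift at both visits then largely cancels in a change analysis. This is a realistic case, but 2.10 does not commit to change scores, and the sentence on graphics does not settle it.

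5. **The lack of masking is disclosed.** It is, and that is to the authors' credit. Disclosure does not remove the bias, and here masking was available.

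**Conclusion.** The concern holds. It rests on a stated design rule (2.9) applied to a single-reader, judgement-based main outcome (2.5.1), not on silence alone. That slides could be coded is an inference from the laboratory handling in 2.4.2.

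What is established is a risk. Neither its size nor its direction can be read from the documents, and bias is not shown to have occurred. The simulated rates are illustrative: a 10% upgrade share hardly matters, while 30 to 40% in one arm at week 6 would roughly triple or quadruple the 5% error in the base case under Mann-Whitney (13.9% and 21.4%). Shifts common to both arms do not inflate the error. The point should be fixed because it affects the main outcome and was avoidable.

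**What to change.** The document reports completed work, with admissions up to December 2019, so the practical remedy is a masked re-read of retained slides, described in 2.9:

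- The laboratory relabels each slide with a random code that hides both arm and visit.
- The clinician reads the slides in random order.
- Scores are locked before the code list is opened.
- The masked scores are used for the main analysis. It would help to report the existing scores beside them, with their agreement.
- Section 2.10 states whether week-6 scores or change is tested, and by which test.

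If the slides were not kept, which the document does not say, name unmasked reading of the main outcome as a major limitation and temper the conclusion on it.

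**Cost:** at most 51 patients × 2 visits × 3 stains = 306 sections, assuming one section per stain, plus relabelling and one clinician's time. No new patient, biopsy or extra reader is needed. If the slides are gone, only wording changes.

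**Limits:** the same reader may recall some slides; coding and random order reduce this but do not exclude it. Coding also does not cure the overlapping CD31 grades, which need their own definition.

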## 2.10. Statistical analysis

Data were analyzed, based upon an intention-to-treat analysis, using the software package SPSS for iOS version 21.0 (SPSS, Inc. Chicago, IL, USA). Kolmogorov-Smirnov test was used to verify the assumption of normality of all continuous variables. Chi-square test was performed to calculate differences between groups and, if applicable, Fisher's exact test for categorical variables. Student's t-test and Mann-Whitney U test were performed for normally and abnormally distributed quantitative variables, respectively. Graphics to evaluate the differences among decrease in bacterial load and cellular proliferation between groups were done using GraphPad® for Mac OS.

